**11.5. Expected accrual rate:**

We expect to accrue up to 3 patients with R/R-AML and/or HR-MDS per month once the study is open. Enrollment is expected to be complete within 12-18 months. The duration of therapy and follow-up period is up to 24 months (excluding any patients that may be eligible to continue on therapy after the trial period per discretion of Io Therapeutics and the PI). Therefore, the total expected duration of the study, including recruitment, therapy, and follow-up, is expected to be a maximum of 50 months.

**11.6. Stratification factors:**

There are no planned stratifications for this protocol.

**11.7. Analysis of secondary endpoints:****Pharmacokinetics:**

In the dose escalation phase, we plan to first determine PK parameters of IRX5183 at baseline and day 14 ( $\pm 3$  days) in the PB and BM compartments. In the dose expansion phase, we will perform confirmatory testing in a subgroup of patients at the same time points. PK analyses will be largely descriptive, using Student's t-tests or Wilcoxon rank sum tests comparing drug concentrations at both time points. We will also assess the peak and trough levels in the PB at the above time points.

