Unlike other retinoids with pan RAR activity, IRX5183 did not induce dermal irritation in a mouse model. However, it does retain the hypertriglyceridemic effect of other retinoids. A receptor-specific retinoid such as IRX5183 may induce fewer adverse effects when compared to a receptor-non-specific retinoid such as ATRA, while retaining the modulation activity of the cell cycle. The clinical use of ATRA has been complicated by the development of ATRA resistance due to pharmacokinetic reasons. Chronic oral ATRA therapy in APL patients results in progressively lower blood levels of ATRA presumably because of autoinduction of metabolism (Adamson, 1996). In contrast, structural features incorporated into the IRX5183 molecule have been designed to make the compound resistant to this degradative catabolism. Full pharmacokinetic evaluation in rats demonstrates that, for the most part, maximal concentrations (Cmax) and area-under-the-curve (AUC) values are not changed between days 8 and 30 at any of the doses tested. Similar evaluations in dogs show that IRX5183 Cmax and AUC values are unchanged between days 7 and 28. This pharmacokinetic profile observed in rats and dogs appears to be retained in humans, where Cmax and AUC values on day 14 were increased relative to day 0 after the first dose (Investigator's Brochure, 2008). Therefore, persistently high blood drug levels should be obtained upon chronic oral dosing with IRX5183.

IRX5183 was studied in an animal model of t(8;21) AML1-ETO, where fetal liver cells were transfected and transduced with AML1-ETO9a plasmids and transplanted into irradiated Ptpcr mice (Chee et al., 2013). The mice developed leukemia by 5 weeks post-transplant. IRX5183 or DMSO was given orally at 45 mg/kg daily six days per week for four weeks. The IRX5183 treated mice had significantly lower total white blood cell counts, peripheral blood blasts, and green fluorescent protein positive cells two weeks after completion of treatment. In addition, they had significantly more maturing intermediate myeloid cells and neutrophils. There was no effect on survival of the mice, but treatment ceased after only four weeks of therapy; after drug withdrawal, the blast cell population expanded and ultimately led to death from leukemia.

[figure not shown]

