IRX5183 has been used in humans in two separate studies. The first was a single-center, phase I trial evaluating the safety, maximum tolerated dose (MTD), and pharmacokinetics of IRX5183 administered daily for a minimum of 4 weeks, performed in patients with refractory malignancies. The starting dose was 60 mg/m^2/day as a single daily dose in the morning based on pre-clinical data. A total of 15 patients were accrued, and 12 completed at least one 4-week cycle of therapy. Due to dose-limiting toxicities (DLTs), the dose was reduced to 30 and then 15 mg/m^2, with 15 mg/m^2 determined to be the MTD. 3 of 4 DLTs were elevated alkaline phosphatase (all in patients with liver metastases and 2 had elevated alkaline phosphatase at baseline). The 4th DLT was grade 3 mucosal inflammation. 10 patients came off study because of progressive disease (PD) and no antitumor activity was observed. The drug was absorbed rapidly and reached peak concentrations approximately 1 to 3 hours following dosing. The terminal elimination half-life ranged from 3.3 to 16.1 hours on the first day of dosing. Based on persistently high drug levels, stable anti-proliferative, pro-differentiation and anti-apoptotic effects could be expected with oral IRX5183.

The second trial evaluating IRX5183 in humans was a randomized, open label, single center phase I/II trial studying peripheral blood progenitor cell (PBPC) mobilization in combination with G-CSF, with intra-patient control and an additional control arm of two mobilizations with G-CSF alone, after high dose chemotherapy in patients with multiple myeloma and lymphoma. For the intra-patient control, each patient underwent 2 mobilizations and mobilization variables were compared between each episode. IRX5183 was given at a dose of 60 mg/m^2 daily and G-CSF was given at a dose of 10mcg/kg daily. 8 patients were accrued to the study and patients were administered IRX5183 60 mg/m^2 daily for up to 28 days. No serious adverse events associated with IRX5183 were reported and no DLT was observed. The conclusion from the study was that IRX5183 and G-CSF in combination was unlikely to benefit poor progenitor cell mobilizers, but it may benefit good mobilizers, particularly if pretreated prior to a second mobilization with G-CSF alone.

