# To be done at baseline, day 14 ( $\pm$  3 days) of cycle 1, after completion of cycle 1, 2, 4, 6, 10, 14, and 18, and at the end of the study.

## Patients will be monitored at least monthly for 6 months after study completion in person, or by phone if patient followed by a local oncologist.

◆ Draw ½ hour before the morning dose and then 2 hours ( $\pm$ 30 minutes) post drug administration on days 1 and 14 ( $\pm$  3 days). On day 14 ( $\pm$  3 days), bone marrow will be obtained for PK about 2 hours post drug (allowed as soon as 1 hour or as long as 4 hours post). May be obtained post cycle 1, only if day 14 BM specimen not available.

▲ Variations of  $\pm$  3 days of the scheduled visit are permitted. Labs may be drawn more frequently if clinically indicated.

An unscheduled visit can occur at any time during the study. The date for the visit and any data generated must be recorded on the appropriate CRF. Source documents for these unscheduled visits must also be maintained.

Pregnancy tests are only for females of childbearing potential. A female of childbearing potential is a sexually mature female who: 1) has not undergone a hysterectomy or bilateral oophorectomy; or 2) has not been naturally postmenopausal for at least 24 consecutive months (i.e., has had menses at any time in the preceding 24 consecutive months).

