## 11. STATISTICAL CONSIDERATIONS

### 11.1. Study design & endpoints:

In the dose-escalation part of the study, there will be 3 dose levels (dose level 1 [DL1] with 50 mg, DL2 with 75 mg, and DL3 with 100 mg), with 1 additional dose level to be only used if excessive toxicity noted at the DL1. There will be no intra-patient dose escalation. Dose-escalation rules are defined through a standard 3+3 algorithm as outlined in Section 5.2.

The phase II expansion part of the study will aim to recruit a total of 27 patients with either R/R-AML or HR-MDS, and there will be an interim analysis after 13 patients for futility through a Simon two-stage minimax design based upon a Type I error rate of 0.05, power of 0.8, response probability of poor drug 0.05, and response probability of good drug of 0.2, based on prior relapsed and refractory AML trials and CTEP data on non-pediatric oncology trials from 2001 to 2012 (Itzykson et al., 2015; Ritchie et al., 2013; Thol et al., 2015; Yoko Korenaga Fukuda, 2014). Stage 1 will enroll 13 patients at the RP2D and will require at least 1 response for

continued enrollment to Stage 2, to reach the total of 27 patients. A total of 4 or more responses out of 27 patients will be considered encouraging evidence for future larger clinical trials of IRX5183.

Response will be defined per IWG criteria as CR, CRi, or PR for AML patients and as CR, CRi, PR, or HI for MDS patients (see definitions in Appendix A) and will be determined with each BM assessment. The composite of these responses across our study population will be referred to as the overall response rate (ORR). Rates of CR, CRi, PR, HI, and the composite endpoint of ORR will be summarized and reported with an exact 95% confidence interval.

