### **11.4. Sample size considerations:**

For the dose-escalation part of the trial, we will enroll up to 18 patients, per standard 3+3 design with 3 DLs (see table 2 in section 5.2). Once we have determined our RP2D, we will proceed to phase II of the trial, where we will recruit an additional 21 R/R-AML or HR-MDS patients at the RP2D, for a total sample size at the RP2D of 27 (inclusive of patients treated at the RP2D in phase I). This sample size was determined using a minimax Simon two-stage design, as described in Section 11.1. Based on prior experience at our institution in this patient population, we will account for a dropout rate of 30%, so we will aim to recruit an additional 8 patients to the dose expansion phase, so that our trial will accrue up to 35 patients to this phase.

In phase II of the trial, the study team will meet regularly to determine whether it is worthwhile to continue enrollment, if an excessive number of patients are unable to complete 2 full cycles of therapy at the RP2D, whether for reasons of DLTs or PD.

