**Pharmacodynamics:**

Biologic correlates include measurement of markers of myeloid differentiation by flow cytometry (e.g. CD15, CD11b), BM blast count, and ANC at the different dose levels in the dose escalation phase and at the RP2D in the expansion phase at the different time points compared to baseline. In addition, we will look at the ratio of ANC to BM blast count as clinical marker for differentiation at the different time points compared to baseline. Statistics will be descriptive and will consist of paired Student's t-tests or Wilcoxon rank sum tests comparing averages between 2 time points (e.g. after induction therapy compared to baseline).

We will furthermore assess *in vivo* changes in detectable chromosomal abnormalities in patients with baseline cytogenetic alterations that define their malignant clones. This will be measured by fluorescent in situ hybridization (FISH) with cells from the individual cellular compartments quantified as a ratio of malignant to non-malignant cells (i.e., mononuclear cells with the cytogenetic finding to those without). Successful differentiation would be expected to result in a decrease in mononuclear cells harboring the cytogenetic abnormality. These results will be summarized using descriptive statistics and exploratory plots will be used to illustrate results.

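### The day-1 versus day-14 drug-level comparison in Section 11.7 has no log scale, within-patient ratio or interval, although the question is a fold change

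*Combined protocol and SAP*

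**What the plan says.** Section 11.7, under Pharmacokinetics, states: "PK analyses will be largely descriptive, using Student's t-tests or Wilcoxon rank sum tests comparing drug concentrations at both time points". It adds that peak and trough blood levels will be assessed at those times. It gives no scale, ratio, dose adjustment or interval; Section 11.7 mentions confidence limits only under clinical activity. For pharmacodynamics, the same section says "Statistics will be descriptive and will consist of paired Student's t-tests or Wilcoxon rank sum tests comparing averages between 2 time points". The t-test is therefore called paired there, but not for drug levels.

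The design facts that bear on this are:

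- Section 11.1: "there will be 3 dose levels (dose level 1 [DL1] with 50 mg, DL2 with 75 mg, and DL3 with 100 mg"; and "There will be no intra-patient dose escalation".
- Section 11.4: "we will enroll up to 18 patients, per standard 3+3 design with 3 DLs".
- Section 10, PK footnote: "Draw ½ hour before the morning dose and then 2 hours" after it, on days 1 and 14. Section 7.8 describes marrow sampling for drug level on day 14 only, or after cycle 1 if that specimen is missing.
- Section 2.5, on the purpose: "Therefore, persistently high blood drug levels should be obtained upon chronic oral dosing with IRX5183". This follows a contrast with ATRA, whose levels fall on chronic dosing, and a report that human peak and AUC values were higher on day 14 than after the first dose.
- Section 2.5, the only information on spread between patients: "The terminal elimination half-life ranged from 3.3 to 16.1 hours on the first day of dosing".

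**The concern.** Resistance to breakdown on repeated dosing is one of the stated reasons for using this drug instead of ATRA. The natural measure is how many times higher or lower a patient's day-14 level is than the same patient's day-1 level. Because the dose is not escalated within a patient, that ratio is free of dose when kinetics are roughly proportional.

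The planned t-test instead yields a mean difference in concentration units. Patients with high levels carry most of the weight, and the result cannot be read as a fold change. In a pooled phase I analysis its size would also depend on how many patients entered each dose level, which in a 3+3 design is decided by toxicity. With at most 18 phase I patients, a p-value without an interval says little about whether exposure was sustained.

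**Working it through.** **No planned figure to reproduce.** The documents give no alpha, power, effect size or variance for this comparison. The phase I maximum does reproduce: 3 dose levels × 6 = 18.

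**Step 1: dose mix (no variance assumption).** Let a patient's day-1 peak be dose × a, where a is that patient's own factor, unrelated to dose. Let the day-14 peak be ρ times the day-1 peak. Then

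- expected raw mean difference = (ρ − 1) × mean(a) × mean dose;
- mean log difference = ln ρ, whatever the doses.

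| Patients at 50/75/100 mg | Mean dose (mg) | Raw difference relative to 50 mg only |
|---|---|---|
| 6/0/0 | 50 | 1.00 |
| 6/6/0 | (300 + 450)/12 = 62.5 | 1.25 |
| 6/6/6 | (300 + 450 + 600)/18 = 75 | 1.50 |
| 3/3/6 | (150 + 225 + 600)/12 = 81.25 | 1.625 |

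The same fold change gives a raw difference 1.5 times larger for 6/6/6 than for 50 mg only.

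**Step 2: power under assumed variability.** Simulation used 5,000 trials per setting, two-sided 0.05, and lognormal, dose-proportional levels. The assumptions were between-patient CV 30, 50 or 80%, within-patient CV 20, 30 or 50%, and day-14/day-1 ratio 1.25, 1.5 or 2. All tests in this table are paired; gains were computed before rounding.

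| Mix | CV between/within | Ratio | Raw | Dose-normalised, no log | Log | Gain, log over raw (points) |
|---|---|---|---|---|---|---|
| 6/6/6 | 50/20% | 1.5 | 1.00 | 1.00 | 1.00 | 0 |
| 6/6/6 | 50/30% | 1.25 | 0.45 | 0.47 | 0.57 | 12 |
| 6/6/6 | 80/50% | 1.5 | 0.46 | 0.48 | 0.68 | 23 |
| 3/3/6 | 80/50% | 2 | 0.65 | 0.68 | 0.90 | 25 |
| 6 at 50 mg | 80/30% | 2 | 0.58 | 0.58 | 0.90 | 33 |

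Over the whole grid the gain was 0 to 23 points at n = 18, 0 to 25 at n = 12, and 2 to 33 at n = 6 on one dose. A second set (20,000 trials, doses spread equally) included falls in exposure. With log SDs of 0.8 between and 0.5 within patients, n = 9 and a ratio of 0.5, power was 41% raw and 74% log in one run, again 33 points. Under no change (n = 12, log SDs 0.6/0.4) the rejection rates were 3.6% raw and 5.3% log, so the log test stays close to its nominal size.

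**Step 3: where the gain comes from.** With n = 12, ratio 1.5 and log SDs 0.6/0.4:

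- mixed doses: 0.44 raw, 0.62 log;
- everyone on one dose: 0.46 raw, 0.62 log.

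The gap is nearly the same without any dose spread. Dose-normalising without logs adds only about 0 to 4 points to a paired test. The gain is therefore almost wholly an effect of the assumed skewness.

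**Step 4: the rank sum option.** Taking logs preserves order, so the rank sum statistic does not change and the missing log costs it nothing. With mixed doses, dose-normalising would add 0 to 30 points to it; at a single dose it adds none. It is an unpaired test and does not by itself estimate a fold change.

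**Step 5: pairing.** This is a separate and larger matter. With CVs 80/20%, n = 12 (3/3/6) and ratio 1.5, power is 0.06 for an unpaired raw t-test and 0.99 for a paired log t-test. Most of that distance is due to pairing: the paired raw test already has 0.90.

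**The case against.** The strongest reply is that the analysis is secondary and described as largely descriptive, with no alpha, power or decision rule, so lost power has limited consequence. That stands, and it is why the point is minor.

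Several stronger readings are tempting but are not supported:

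- **A definite power loss.** A reader might infer that the plan forfeits a known amount of power. The documents give no spread of drug levels. The half-life range (16.1/3.3, about 4.9-fold) is not the spread of a 2-hour level taken inside the 1 to 3 hour window of peak concentration in Section 7.8. At low variability the loss is 0.
- **Dose spread as the cause.** Step 3 shows that it contributes little in a paired test. It matters for the size of a pooled raw difference, and for power mainly if the test is unpaired.
- **Pooling as planned.** Section 11.7 does not say that doses are pooled. The phase I list in Section 11.3 opens with PK and ends by referring to the separate dose levels, which may mean PK is reported by dose. Phase II testing is at the recommended phase 2 dose, so the dose-mix point concerns phase I.
- **Non-significance as proof of stability.** Nothing in the documents says a non-significant result would be read that way. It is a risk of giving no interval, and not a stated intention.

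The power figures also assume a paired test, which the PK text does not state. They compare scales and do not measure the plan exactly as written.

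**Conclusion.** The point holds in a limited form. Section 11.7 specifies tests on drug concentrations without a log scale, a within-patient ratio or an interval, while the question is one of fold change. Two consequences can be stated:

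- If phase I doses are pooled and exposure is proportional to dose, the raw mean difference changes with the dose mix, for example 1.5-fold between 6/6/6 and 50 mg only. This needs no variance assumption.
- Against a paired raw-scale t-test, a paired log-scale t-test gains 0 to about 33 points of power, depending wholly on assumed lognormal variability, effect size and n.

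The more secure benefit is interpretability: an estimated ratio with an interval answers the question in Section 2.5, and a p-value on raw concentrations does not. Severity is low because the analysis is secondary and largely descriptive.

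**What to change.** Replace the test sentence in Section 11.7, Pharmacokinetics, with wording such as:

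> The 2-hour post-dose (peak) plasma concentration will be analysed on the natural-log scale, paired within patient. The day-14 to day-1 geometric mean ratio will be reported with a 95% confidence interval, pooled and by dose level. The day-14 marrow-to-blood peak ratio will be summarised in the same way. The day-1 pre-dose sample is excluded from log-scale analysis; day-14 troughs will be summarised descriptively by dose level. The conclusion on sustained exposure will rest on the interval for the ratio.

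The interval is exp(mean d ± t × s/√n), where d is each patient's log difference, s its standard deviation and t the 97.5% point on n − 1 degrees of freedom. The day-1 pre-dose sample must be left out because it precedes the first dose: its expected level is zero and its log is undefined.

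The cost is a few sentences, with no new samples, visits or patients. There are two small downsides. Values below the assay limit need a stated handling rule. Pooling assumes a similar ratio at each dose, which the by-dose display lets readers check. Stating the pairing also removes the difference from the pharmacodynamic paragraph.

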**Pharmacodynamics:**

Biologic correlates include measurement of markers of myeloid differentiation by flow cytometry (e.g. CD15, CD11b), BM blast count, and ANC at the different dose levels in the dose escalation phase and at the RP2D in the expansion phase at the different time points compared to baseline. In addition, we will look at the ratio of ANC to BM blast count as clinical marker for differentiation at the different time points compared to baseline. Statistics will be descriptive and will consist of paired Student's t-tests or Wilcoxon rank sum tests comparing averages between 2 time points (e.g. after induction therapy compared to baseline).

We will furthermore assess *in vivo* changes in detectable chromosomal abnormalities in patients with baseline cytogenetic alterations that define their malignant clones. This will be measured by fluorescent in situ hybridization (FISH) with cells from the individual cellular compartments quantified as a ratio of malignant to non-malignant cells (i.e., mononuclear cells with the cytogenetic finding to those without). Successful differentiation would be expected to result in a decrease in mononuclear cells harboring the cytogenetic abnormality. These results will be summarized using descriptive statistics and exploratory plots will be used to illustrate results.

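### The ANC-to-marrow-blast ratio has no stated scale or zero-blast rule, and neither test named for it is a sound paired analysis of a skewed ratio

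*Combined protocol and SAP*

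**What the plan says.** Section 11.7, Pharmacodynamics, lists flow-cytometry markers, marrow blast count and ANC, each compared with baseline. It then adds a derived marker, the "ratio of ANC to BM blast count as clinical marker for differentiation", again at each time point against baseline. For the whole group, "Statistics will be descriptive and will consist of paired Student's t-tests or Wilcoxon rank sum tests comparing averages between 2 time points".

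Neither that paragraph nor the rest of section 11 states whether the ratio is transformed, what is done when the blast count is zero, or how the choice between the two tests is made. No alpha, power or sample size is attached to the ratio.

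**The concern.** The denominator is the quantity the drug is meant to reduce. In Appendix A1 an AML remission needs marrow blasts below 5%, and in Appendix A2 an MDS complete remission needs 5% or fewer. Low denominators are also possible at baseline. Section 3.1 admits transfusion-dependent INT-1 or intermediate MDS without excess blasts, and CMML or MDS/MPN on karyotype or proliferative features, with no minimum blast percentage.

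A ratio of this kind is strongly right-skewed, and the two named tests handle that differently. A t-test on untransformed ratios is driven by the few largest values and has no value to use at 0% blasts. The rank sum test is not driven by extremes, but it treats baseline and follow-up as independent samples and discards the pairing. Leaving the choice open also lets it be made after the data are seen.

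Section 8.1 treats biologic activity as essential to interpreting clinical activity. The exploratory assessments in 11.7 relate differentiation measures, including ANC and marrow blasts, to response and survival. An unstable summary would make the marker harder to read in that role.

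**Working it through.** **1. The plan's own figure.** No figure is stated for the ratio. The only powered calculation is for response, with a "Type I error rate of 0.05, power of 0.8, response probability of poor drug 0.05" and a "response probability of good drug of 0.2". Section 11.1 says "Stage 1 will enroll 13 patients at the RP2D", and 11.4 plans "for a total sample size at the RP2D of 27". The rule of at least 1 response in 13 and at least 4 in 27 gives exact alpha 0.0416, power 0.801 and early-stop probability 0.95^13 = 0.513 under the poor-drug rate. The 27 therefore reproduces, but it says nothing about the ratio. It is used below only as the number of pairs, an upper figure if marrows are missing.

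**2. Undefined values.** Assume a 500-cell differential and a true 0.3% blasts in a cleared patient. The chance of reading zero is 0.997^500 = 0.223. If 5% of patients clear, the chance of at least one undefined ratio is 1 − (1 − 0.05 × 0.223)^27 = 26% at n=27, and 14% at n=13. If 20% clear, it is 71% and 45%.

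**3. Leverage.** A patient going from ANC 0.5 with 20% blasts (0.025) to ANC 1.5 with 1% blasts (1.5) has a 60-fold rise. Now let 26 patients go from 0.8/20 to 1.6/14. Each changes by 0.1143 − 0.0400 = 0.0743, in total 1.931. The 27th goes from 0.8/20 to 1.6/x:

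| x (% blasts) | Change in the 27th patient | Share of the raw mean change | Geometric-mean fold change, all 27 |
|---|---|---|---|
| 5 | 0.28 | 0.28/2.211 = 13% | 2.97 |
| 1 | 1.56 | 1.56/3.491 = 45% | 3.15 |
| 0.2 | 7.96 | 7.96/9.891 = 80% | 3.34 |

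The geometric mean barely moves while the raw mean is taken over by one patient.

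**4. Power without any blast clearance.** Assumptions: two-sided 0.05; baseline blasts lognormal, median 20% (log-SD 0.7, minimum 1%); baseline ANC lognormal, median 0.8 (log-SD 0.8); log ratio change normal with mean ln 2 and SD 1. For the log-scale paired t-test the noncentrality is (ln 2/1) × √27 = 3.60, against a critical value of 2.056 on 26 degrees of freedom, so exact power is 93%. At n=20 it is 84%. The other two tests were simulated, with error of about 1 percentage point:

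| Pairs | Raw paired t | Log paired t | Rank sum |
|---|---|---|---|
| 27 | 73% | 93% | 48–49% |
| 20 | 60% | 84% | 31% |

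**5. Power with other assumptions.** Take ANC doubled, blasts multiplied by 0.7, and log-SD of change 0.8 for each, with zero counts set to half a cell. Rank-test figures here carry an error of up to about 2.5 points.

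| Pairs, share cleared | Raw paired t | Log paired t | Signed-rank | Rank sum |
|---|---|---|---|---|
| 27, none | 75% | 99.7% | 100% | 90% |
| 27, 5% | 45% | 100% | 100% | 94% |
| 13, none | 42% | 88% | 88% | 48% |
| 13, 5% | 26% | 89% | 92% | 53% |

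The raw t-test trails the log-scale test throughout. The rank sum test falls below the raw t-test in step 4 and above it in step 5, and it is below the paired log-scale test in both.

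**The case against.** The strongest reply is that the plan does not commit to a t-test on untransformed ratios. The raw scale is inferred from silence, and the same sentence offers a Wilcoxon test, which can rank a positive ANC over 0% blasts as the largest value. That stands, and it is why the instability is stated only for the raw t-test branch. It does not rescue the sentence as a whole, because the Wilcoxon test named is the unpaired one. A paired signed-rank test would recover the power, but the plan does not name it.

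A reader might infer that the best responders will be dropped and the marker biased toward no effect. The documents do not support that. They contain no exclusion rule, an undefined ratio needs a recorded 0%, and a remission with blasts just under 5% gives a finite ratio. Section 2.3 reports no complete remissions in the two earlier companion trials, so clearance may be uncommon. Nor is clearance needed for the power loss: step 4 contains none, and the gap there is ordinary skewness.

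It is also fair that the statistics are labelled descriptive, that no decision rule uses the ratio, and that ANC and blast count are each analysed separately (11.3 and 11.7). A badly behaved ratio would not hide those results. All of this limits the consequence.

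**Conclusion.** The concern holds in a limited form. Scale, zero-blast handling and choice of test are unspecified, and neither named option is a sound paired analysis of this ratio. At n=27, for a 2-fold rise with log-SD 1, power is about 73% for the raw t-test and 48% for rank sum, against 93% for a paired test on the log scale. One near-cleared patient in 27 can supply most of the raw mean change.

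The direction of the raw-versus-log comparison was the same under every non-null assumption tried. The size depends on assumed spreads, effects, cell counts and clearance rates, none of which the documents give. The figures compare one analysis with another; they are not a shortfall against a power the plan promised. The documents do not support reading this as a certain loss of signal, or as rank sum always being the worse of the two. Importance is low: a descriptive secondary marker is affected, and the primary endpoint and phase II sample size are not.

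**What to change.** In 11.7, Pharmacodynamics, state that the ratio is analysed as the within-patient change in log(ANC) minus log(blasts). Set a floor in advance for zero or unreportable values of either component, for example 0.5% for blasts and the laboratory's lowest reportable ANC, with one alternative floor as a sensitivity analysis. Name one test in advance: the paired t-test on the log change, or the Wilcoxon signed-rank test on the log change. Replace rank sum by signed-rank for the paired comparisons in that paragraph. Report the geometric-mean fold change with a 95% CI beside the ANC and blast changes already planned.

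The cost is a sentence or two of text and no new data. The downside is that any floor is arbitrary, and the alternative floor shows how much it matters.
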